9.3.2 Secondary Endpoint 2: HIV-1 drug resistance mutations among participants who acquire HIV-1

Consistent with the secondary objective to evaluate HIV-1 drug resistance mutations among participants who acquire HIV-1 in the trial, secondary endpoint 2 is the proportion of HIV-1 seroconverters with drug resistant mutations.

Assessments

HIV viral genotyping will be performed on all HIV-1 seroconverters.

Statistical methods

The analysis of HIV-1 drug resistance will be primarily descriptive in nature, and will depend on the pattern of resistance-associated mutations (RAMs) observed in the HIV-1 seroconverters. The Stanford NNRTI Resistance Mutation Scores of Drug Resistance Mutations in HIV-1 (database version 8.4 - dated 2017-06-16) is provided in Appendix 4.

The number of RAMs observed will be listed by participant, and a frequency tabulation of individual RAMs associated with the various classes of antiretrovirals (Protease Inhibitors [PIs], Nucleoside Reverse Transcriptase Inhibitors [NRTIs] and Non-nucleoside Reverse Transcriptase Inhibitors [NNRTIs]) will be produced. The proportion of HIV-1 seroconverters with at least one HIV-1 drug resistant mutation will be presented overall, and by research centre, if possible, with corresponding 95% confidence intervals (using the Fisher's exact test).

If the data allows, the following frequency tabulations will be created:

- The number (and percentage) of participants who had a resistance test performed (pre-seroconversion, at seroconversion and at the Exit visit.)

- Reasons why a resistance test was not performed (if available in the database.)
- The number (and percentage) of participants with each individual mutation by class (NNRTI, NRTI, major PI.)
- The number (and percentage) of participants with 0, 1, 2, and ≥ 3 mutations by class (NNRTI, NRTI, major PI.)
- The number (and percentage) of participants with different mutational patterns (including single mutations), by class (NNRTI, NRTI, major PI.)
- Additional mutations (e.g. those selected by dapivirine in vitro but not included in the Stanford HIV database set) will be described.

In addition, for each NNRTI drug, the resistance mutation scores for NNRTIs efavirenz, etravirine, nevirapine and rilpivirine, will be calculated according to the Stanford database version 8.4, dated 2017-06-16 (see Appendix 4), per genotype by summing the individual scores associated with individual mutations (and the additional scores for combinations of mutations where applicable.) Based on the resistance mutation score, virus from participants will be classified as susceptible, potential low-level resistant, low-level resistant, intermediate resistant or high-level resistant for each NNRTI drug, based on the following cut-offs:

NNRTI resistance mutation score	Level of resistance
<10	Susceptible
10 - <15	Potential low-level resistant
15 - < 30	Low-level resistant
30 - < 60	Intermediate resistant
≥ 60	High-level resistant

For each approved NNRTI drug (efavirenz, etravirine, nevirapine and rilpivirine), descriptive statistics will be presented on the total NNRTI resistance mutation score and a frequency tabulation will be presented on the resistance level.

Note: Only results at time of HIV-1 seroconversion will be included in tabulations. Listings of all individual data will be created and will include all participant resistance assessments.

These analyses will be performed overall, by HIV-1 RNA level at HIV-1 seroconversion (≥ 2000 copies/mL, < 2000 copies/mL), treatment schedule (A, B or C) and by HIV-1 subtype (C, other).

There will be an additional analysis to determine the number and timing of samples analysed prior to and after HIV-1 seroconversion. Any changes of genotype between the prior- and after- HIV-1 seroconversion samples will be described.

Finally, the primary analysis will be repeated for the Virology Population, for all samples analysed at any time during the period of the first positive HIV-1 RNA visit and the Exit visit. This is to ensure that all mutations are accounted for.

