Any	n (%) ^b		X (X.X)	X (X.X)	X (X.X)
One	n (%) ^b		X (X.X)	X (X.X)	X (X.X)
Two	n (%) ^b		X (X.X)	X (X.X)	X (X.X)
Three	n (%) ^b		X (X.X)	X (X.X)	X (X.X)
...
Average	Mean		XX.X	XX.X	XX.X
NRTI mutations					
None	n (%) ^a		X (X.X)	X (X.X)	X (X.X)
Any	n (%) ^b		X (X.X)	X (X.X)	X (X.X)
One	n (%) ^b		X (X.X)	X (X.X)	X (X.X)
Two	n (%) ^b		X (X.X)	X (X.X)	X (X.X)
Three	n (%) ^b		X (X.X)	X (X.X)	X (X.X)
...
Average	Mean		XX.X	XX.X	XX.X
Major PI mutations					
None	n (%) ^a		X (X.X)	X (X.X)	X (X.X)
Any	n (%) ^b		X (X.X)	X (X.X)	X (X.X)
One	n (%) ^b		X (X.X)	X (X.X)	X (X.X)
Two	n (%) ^b		X (X.X)	X (X.X)	X (X.X)
Three	n (%) ^b		X (X.X)	X (X.X)	X (X.X)
...
Average	Mean		XX.X	XX.X	XX.X

Programmers Notes:

Please repeat table for the following subgroups: HIV-1 RNA level: HIV-1 RNA level: ≥ 2000 copies/mL, < 2000 copies/mL; HIV-1 subtype (C / Other) and Schedule A, B or C
- Table 14.3.7.13.2 will be similar to Table 14.3.7.13.1 but the heading and analysis will be based on Any Timepoint

HIV-1 = Human immunodeficiency virus type 1; NNRTI = Non-nucleoside reverse transcriptase inhibitor ; NRTI = Nucleoside reverse transcriptase inhibitor; PI = Protease inhibitor

Percentages are calculated out of the number of participants (per IPM 027 treatment) ^a In the virology population ^b Reported HIV-1 drug resistance-associated mutation

Resistance-associated mutations were defined using the Stanford HIV database algorithm Version 8.4

Table 14.3.7.14.1
Summary of Mutational Patterns of Resistance-Associated Mutations at Seroconversion Timepoint
Virology Population

Subgroup: All IPM 032 participants		IPM 027 Dapivirine (N=XXX)	IPM 027 Placebo (N=XXX)	IPM 032 Overall (N=XXX)
Mutation Score Classification	Statistic			
Resistance categorization score	N	XX	XX	XX
Susceptible				
Potential low-level resistant	n (%) ^a	X (X.X)	X (X.X)	X (X.X)
Low-level resistant	n (%) ^a	X (X.X)	X (X.X)	X (X.X)
Intermediate resistant	n (%) ^a	X (X.X)	X (X.X)	X (X.X)
High-level resistant	n (%) ^a	X (X.X)	X (X.X)	X (X.X)

Programmers Note:

Please repeat table for the following subgroups: HIV-1 RNA level: HIV-1 RNA level: \geq 2000 copies/mL, < 2000 copies/mL; HIV-1 subtype (C / Other); Schedule A, B or C
- Table14.3.14.2 will be similar to Table14.3.14.1 but the analysis and header will be based on Any Timepoint

HIV-1 = Human immunodeficiency virus type 1; NNRTI = Non-nucleoside reverse transcriptase inhibitor; NRTI = Nucleoside reverse transcriptase inhibitor; PI = Protease inhibitor

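### The resistance-level table shell (14.3.7.14.1/.2) drops the per-drug split and score statistics that SAP 9.3.2 promises, and its percentages are taken out of a population that includes uninfected women

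*SAP*

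**What the plan says.** SAP 9.3.2 (Secondary Endpoint 2, Statistical methods) builds a score per genotype for each of four NNRTIs "by summing the individual scores associated with individual mutations", with extra points for certain combinations. It then states that "virus from participants will be classified as susceptible, potential low-level resistant, low-level resistant, intermediate resistant or high-level resistant for each NNRTI drug". The five levels are set by the score: below 10, 10 to below 15, 15 to below 30, 30 to below 60, and 60 or more. The reporting commitment is also per drug: "For each approved NNRTI drug (efavirenz, etravirine, nevirapine and rilpivirine), descriptive statistics will be presented on the total NNRTI resistance mutation score", together with a frequency table of resistance level.

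The matching shell is Table 14.3.7.14.1 in SAP Appendix 1, with 14.3.7.14.2 as its any-timepoint version. Under the row heading "Mutation Score Classification" it has one block, "Resistance categorization score", holding the five levels. The columns are the two IPM 027 arms and IPM 032 overall. The programmer note repeats the table by HIV-1 RNA level and by "HIV-1 subtype (C / Other); Schedule A, B or C". Drug is not among the repeats. The footnote attached to the level rows takes percentages out of the virology population. A second footnote, for successful assessments, is defined but attached to no row.

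SAP Section 5 (Virology Population) defines that population as everyone in the m-ITT population except women who seroconverted after the last product use visit.

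**The concern.** The text and the shell describe different tables. Under the text a woman has four resistance levels, one per drug. The shell has room for one and gives no rule for reducing four to one. It also has no rows for the promised score statistics. A programmer working from the shell would have to make a choice that the SAP does not state.

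The denominator is a separate fault. A resistance level exists only for a woman with HIV-1 and a successful genotype. Dividing by a population made up largely of uninfected women turns the share of seroconverters at each level into a share of nearly the whole trial. Every percentage would then look reassuringly small whatever the resistance pattern.

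**Working it through.** **Inputs.** The cut-offs are from SAP 9.3.2. The scores by drug are from Appendix 3 (8.3) of the virology addendum SAP: 50 single-mutation rows, of which 49 count. V106I is bracketed there because it is scored only in a later database version. Planned enrolment of about 1400 is from SAP 3.2.

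**The documents' own figure.** The addendum's example is K101E + Y181C for efavirenz: 15 + 30 + 5 = 50, as stated. For the other drugs the same genotype gives:
- etravirine: 15 + 30 + 5 = 50
- nevirapine: 30 + 60 + 5 = 95
- rilpivirine: 45 + 45 + 0 = 90

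This woman is intermediate for two drugs and high-level for two. No single row of the shell describes her.

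**Single mutations.** Each of the 49 rows was mapped to a level for each drug, and the lowest and highest levels were compared.

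| Spread across the four drugs | Mutations |
|---|---|
| Same level for all four (K101P, V179D, V179E, F227C) | 4 |
| One adjacent level apart | 17 |
| More than one level apart, but not the full range | 19 |
| Susceptible to high-level | 9 |
| Total | 49 |

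So 17 + 19 + 9 = 45 of 49 differ by drug (46 of 50 with V106I). The nine that span the full range are K103H, K103N, K103S, K103T, V106A, V106M, Y188C, Y188F and Y188H. K103N, for example, scores 60 for efavirenz and nevirapine and 0 for etravirine and rilpivirine.

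**Denominator.** Let G be the number of successfully genotyped seroconverters, V the size of the virology population, and x the number at a given level.
- Share among those with a result: x/G
- Share under the shell's footnote: x/V = (x/G) × (G/V)

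Every percentage is therefore multiplied by G/V. The documents give no expected G. If V is close to the planned 1400 (an assumption), one woman contributes 1/1400 = 0.07% and two contribute 2/1400 = 0.14%. At the one decimal place set in SAP 6.6, both print as 0.1%. If every genotyped seroconverter were high-level resistant, that row would show G/1400 rather than 100%.

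**The case against.** The strongest reply is that the governing text is already right. SAP 9.3.2 is per drug throughout, SAP Section 1 treats the shells as supporting material, and nothing instructs a programmer to pool drugs. Listing 16.2.8.13 gives score and classification for each participant and each drug, and with few seroconverters it can be tabulated by hand. All of this stands, and it confines the drug fault to the shell. It does not make the shell consistent with the text.

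A reader might infer that the plan gives each woman one pooled level. That is read from the layout only: the shell fails to show the drug, but it does not state a pooling rule. Nor does 45 of 49 mean that most carriers could land at opposite ends of the table. Seventeen of the 45 move by a single adjacent level and only nine cover the full range. These are also unweighted database rows, not women.

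The shell may have lost rows in text conversion: the susceptible row shows no statistic, and one footnote has nowhere to attach. However, the programmer note reads as complete and still omits drug.

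On the denominator, one could say that the virology population means seroconverters, as Section 3.2 of the addendum defines it. The main SAP does not define it that way, and its own Listing 16.2.4.2, headed with that population, allows a non-seroconverter status. The main SAP definition governs this table.

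**Conclusion.** Wrong as written, in the summary table shell. The per-drug tables and the score statistics promised in SAP 9.3.2 have no place in Table 14.3.7.14.1/.2. On the documents' own scores the choice of drug changes the level for 45 of 49 single mutations, and takes 9 of them from susceptible to high-level. The denominator is the part that most plainly changes a reported result, because every percentage shrinks by the factor G/V.

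A reader might go further and conclude that secondary endpoint 2 is compromised. The documents do not support that. SAP 9.3.2 defines the endpoint as the proportion of seroconverters with resistance mutations, and the score levels are an additional analysis. That proportion and Listing 16.2.8.13 are unaffected.

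The counts assume that the addendum's score table is the one to be applied. It is headed version 8.4 but dated 18 July 2018, while SAP 9.3.2 cites version 8.4 of 16 June 2017. Appendix 4 of the main SAP, which 9.3.2 cites for the scores, shows only mutation lists in the text available. The denominator figures assume a virology population near the planned 1400.

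**What to change.** 1. Repeat Table 14.3.7.14.1 and .2 for efavirenz, etravirine, nevirapine and rilpivirine, each with the five levels, keeping the existing subgroup repeats.
2. Take percentages out of seroconverters with a successful genotype at the timepoint concerned, using the footnote for successful assessments that is already defined.
3. Add n, median and range of the total score for each drug.
4. If a single overall figure is wanted, label it 'highest level to any of the four NNRTIs'.
5. State which dated score table applies, so that the two version 8.4 dates agree.

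If the table has already been produced, confirm which drug or rule and which denominator were used, and reissue it. No new data are needed, because the per-drug scores and levels are already in Listing 16.2.8.13. The cost is a revised shell and some reprogramming. The denominator change alters reported percentages, so it should be recorded as more than a formatting change.

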9.4 Exploratory Endpoints

9.4.1 Exploratory Endpoint 1: Participant report of feasibility of 3-monthly clinical follow-up schedule

Consistent with exploratory objective 1, exploratory endpoint 1 is the participant report of feasibility regarding a 3-monthly clinical follow-up schedule (Participant Questionnaire).

Assessments

Participants will complete a Participant Questionnaire at all trial visits until the last product use visit. In particular, the following items will be captured:

Participant Questionnaire Part A (month 1, 2 and 3):

Item 1: As per investigator decision are you coming to the research centre next month or in three months for your next visit?

Item 2: Will you take your extra rings with you today or will you come back to the research centre each month to pick up your new ring?

Item 3: What are your reasons for leaving the rings at the research centre today?

Participant Questionnaire Part B (month 2 and 3):

Item 10: If you were not in a study, would you prefer to come to the health care clinic / provider for new rings each month, or every three months?

Item 11: If you were not in a study, would you prefer to come to the health care clinic / provider for an HIV test each month, or every three months?

Participant Questionnaire (3 month follow-up):

Item 1: Will you take your extra rings with you today or will you come back to the research centre each month to pick up your new ring?

Item 2: What are your reasons for leaving the rings at the research centre today?

Item 16: If you were not in a study, would you prefer to come to the health care clinic / provider for new rings each month, or every three months?

Item 17: If you were not in a study, would you prefer to come to the health care clinic / provider for an HIV test each month, or every three months?

Participant Questionnaire (last product use visit):

Item 1: When you were doing your three monthly visits, did you take your extra rings with you or did you come back to the research centre each month to pick up your new ring?

Item 2: What were your reasons for leaving the rings at the research centre?

Item 16: If you were not in a study, would you prefer to come to the health care clinic / provider for new rings each month, or every three months?

Item 17: If you were not in a study, would you prefer to come to the health care clinic / provider for an HIV test each month, or every three months?

At all trial visits and the last product use visit, the RL CRF will be completed, indicating the rings dispensed at each trial visit (items 1 and 2) and the used / unused rings returned at each trial visit (items 7 and 8).

Statistical methods

The analysis of feasibility of the 3-monthly clinical follow-up schedule will be primarily descriptive in nature, and will include absolute and relative frequencies for each trial visit for Participant Questionnaire items listed above, overall and by Visit Schedule (A, B or C). In particular, the number and percentage of women opting not to receive two additional rings at the 3-monthly clinical follow-up schedule will be reported.

The proportion of returned rings (used and unused) during the 3-monthly clinical follow-up schedule will also be reported. This will be calculated as the number of used/unused rings returned divided by the number of rings dispensed.

9.4.2 Exploratory Endpoint 2: Correlation between dapivirine residual amounts in returned used vaginal rings and/or drug concentrations, and results from visual inspection of returned vaginal rings

Consistent with exploratory objective 2, exploratory endpoint 2 is the dapivirine ring residual levels in returned used vaginal rings and/or dapivirine concentrations in plasma and/or vaginal fluid (not assayed) in correlation with results from the visual inspection of the returned used vaginal rings by research staff.

Assessments

At all trial visits and the last product use visit, the RL CRF will be completed, indicating the rings dispensed at each trial visit (items 1 and 2) and the appearance of used/unused rings returned at each trial visit (items 7, 8 and 9).

Residual levels of dapivirine in used rings will be determined for all participants receiving IP at each trial visit.

Statistical methods

The correlation between the amount of corrected residual dapivirine in the used vaginal rings and the corresponding results from the visual inspection of the returned used vaginal rings, will be explored descriptively by producing summary statistics and

a corresponding scatter plot of the dapivirine levels for each category of appearance and colour of the returned ring.

9.4.3 Exploratory Endpoint 3: Proportion of participants opting for HIV rapid tests at the research centre between scheduled 3-monthly visits

Consistent with exploratory objective 3, exploratory endpoint 3 is the proportion of participants opting for HIV rapid tests at the research centre between scheduled 3-monthly research centre follow-up visits.

Assessments

Trial participants will have HIV rapid tests performed at the research centre at all trial visits until the last product use visit, and at the exit visit, 1-2 months after ring discontinuation, and as needed.

Statistical methods

The proportion of participants undergoing HIV rapid tests at the research centre between scheduled 3-monthly follow up visits will be calculated as the number of participants with at least one HIV rapid test performed at an unscheduled visit divided by the total number of participants with at least one HIV rapid test performed at any visit.

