Dispense one vaginal ring to participants during monthly visits and three vaginal rings during 3-monthly visits (or dispense as arranged with the participant) and provide vaginal ring use and storage instructions (refer to Sections 5.13 and 6.4).

- j. Instruct the participant to insert the vaginal ring during monthly visits. Once the 3-monthly trial visit schedule commences, one ring will be inserted at the research centre and two additional rings will be dispensed for the participant to take home (or dispense as arranged with the participant (refer to Section 5.14).

- k. Collect and review the diary card(s) and provide a new diary card(s) if applicable (refer to Section 5.19).

- l. Administer the Participant Questionnaire at every trial visit (refer to Section 5.16).

- m. Provide adherence counselling, including adherence to trial visit schedule and requirements, and vaginal ring adherence (refer to Section 5.15). Participants will be instructed to keep the ring inserted for a period of one month. Adherence counselling will include information on actions that should be taken in the event of expulsion or removal. If the ring comes out or is removed during this period, the participant should wash her hands, rinse the ring thoroughly in clean water and re-insert it.

- n. Provide contraceptive counselling and contraceptives, if necessary (refer to Section 5.5).

- o. Provide HIV/STI risk reduction counselling; including provision of male condoms if the participant wishes to receive them (refer to Section 5.3.2).

- p. The following procedures are not required, but may be conducted if clinically indicated: physical and pelvic examination, cervicovaginal sample collection for STI testing, provision of treatment and/or referral for STIs and other findings, laboratory testing for safety assessments, urine dipstick analysis (microscopy only if clinically indicated) and cervical sample collection for cytology (if no result is evident within the previous year, or abnormal at last cervical cytology).

- q. Schedule the next visit.

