- Proportion of returned rings (used and unused) during the 3-monthly clinical follow-up schedule.
- Dapivirine residual amounts in returned used vaginal rings and/or dapivirine concentrations in blood and/or vaginal fluid.
- Visual inspection of the returned used vaginal rings by research centre staff.
- Number of participants undergoing HIV rapid tests at the research centre between scheduled 3-monthly research centre follow-up visits.
- Qualitative data regarding ring acceptability and self-reported patterns of ring use.

Note: Although collected and stored, blood and vaginal fluid samples were not analysed for dapivirine, as dapivirine concentrations were found in the Phase III program to have limited value as adherence measures. There is currently no biomarker to indicate whether the ring was used at the time of an HIV risk event; the best measure of ring use during the prescribed 1-month use period is dapivirine ring residual levels in used rings.

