In instances where the date of IP initiation, *i.e.* the start date of ring use, is missing or unknown, the missing date will be imputed with the date of the enrollment visit.

In accordance with the protocol, each scheduled visit has a window period of \pm 7 days. If the participant does not return to the research centre for a scheduled visit prior to the start of the trial window of the next visit, the visit will be considered missed. If a participant presents for a visit outside the window for a scheduled trial visit, but prior to the start of the window for the next visit, it will be treated as a late visit. Missed visits and late visits will be documented as protocol deviations (refer to Section 7.2). Data recorded at late visits will be analysed as pertaining to the scheduled visit. Unscheduled visits may be performed at any time during the trial. If an unscheduled visit takes place within any given window period and any repeat observations are made within the given window period, the repeat values will be captured as pertaining to the unscheduled visit. Data from scheduled and unscheduled visits will be shown in the participant listings, and listings will be appropriately labelled when data arise from unscheduled visits. Data from scheduled visits will be presented in the summary tables.

Visit Schedule A will consist of participants who attend Trial Month Visits 1, 4, 7, 10, 13, and 16/Exit; Visit Schedule B will consist of participants who attend Trial Month Visits 1, 2, 5, 8, 11, 14, and 17/Exit; and Visit Schedule C will consist of participants who attend Trial Month Visits 1, 2, 3, 6, 9, 12, and 15/Exit.

Tables, figures, and listings of trial results will accompany the text of the CSR. Listings of all clinical data recorded in the CRFs will be provided, except for those CRFs which are used for administrative purposes, such as the Participant Encounter Form (PEN) and the End of Trial Inventory (ETI). Listings will be sorted by research centre and participant identification number (PID), and key variables such as visit date and/or trial visit number will be presented in each listing.

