HIV-1 = Human immunodeficiency virus type 1; IP = Investigational product

Table 14.3.7.16
Pregnancy Test Results
Safety Population

Subgroup: All IPM 032 participants

Visit	Pregnancy Result	Statistic	Centre 01			...	All Centres		
			IPM 027 Dapivirine (N=XXX)	IPM 027 Placebo (N=XXX)	IPM 032 Overall (N=XXX)		IPM 027 Dapivirine (N=XXX)	IPM 027 Placebo (N=XXX)	IPM 032 Overall (N=XXX)
Trial Month X / LPUV / All visits	Positive / Negative	n (%) ^a	X (X.X)	X (X.X)	X (X.X)	...	X (X.X)	X (X.X)	X (X.X)
		n (%) ^a	X (X.X)	X (X.X)	X (X.X)		X (X.X)	X (X.X)	X (X.X)

^aPercentages are calculated out of the number of participants in the safety population per centre and IPM027 treatment

Centre 01: Madibeng Centre for Research (MCR); Centre 02: MatCH Research Unit (MRU); Centre 04: Qhakaza Mbokodo (QM);

Centre 06: MRC/UVRI & LSHTM Uganda Research Unit (MRC/UVRI); Centre 07: Desmond Tutu HIV Foundation (DTHF), Masiphumelele; Centre 08: Ndlovu Care Group (NCG)

Table 14.3.8.1
Concomitant Medication
Safety Population

	Statistic	Centre 01 (N=XXX)	Centre 02 (N=XXX)	...	Centre 08 (N=XXX)	All Centres (N=XXX)
Participants with a reported concomitant medication	n (%) ^a	X (X.X)	X (X.X)	...	X (X.X)	X (X.X)
ATC Level 2 Preferred name	n (%) ^b	X (X.X)	X (X.X)	...	X (X.X)	X (X.X)
...						

Percentages are calculated out of the number of participants (by centre) ^a In the safety population ^b Reported concomitant medication

Concomitant medication is defined as any medication taken in conjunction with the investigational product (IP). This includes any medication that started after the first insertion of the IP, or started before the first insertion of the IP but ended on/after the first insertion of the IP.

Medications were coded using WHO DDE (version June 2017)

Centre 01: Madibeng Centre for Research (MCR); Centre 02: MatCH Research Unit (MRU); Centre 04: Qhakaza Mbokodo (QM);

Centre 06: MRC/UVRI & LSHTM Uganda Research Unit (MRC/UVRI); Centre 07: Desmond Tutu HIV Foundation (DTHF), Masiphumelele; Centre 08: Ndlovu Care Group (NCG)

Table 14.6.1
Participant Report, Feasibility of 3-Monthly Clinical Follow-Up Schedule
Safety Population

Visit Question of Interest Response	Statistic	Schedule A (N=XXX)	Schedule B (N=XXX)	Schedule C (N=XXX)	All Schedules (N=XXX)
Trial Month X					
Number of used/unused rings returned	m	XXX	XXX	XXX	XXX
Number of rings dispensed	M	XXX	XXX	XXX	XXX

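### The returned-ring proportion has no defined denominator, and its table shell leads to a ratio of two different sets of rings

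*SAP*

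**What the plan says.** Protocol 2.2 and SAP 2.4 both list this measure among the assessments of the exploratory endpoints; the SAP's wording is "Proportion of returned rings (used and unused) during the 3-monthly clinical follow-up schedule". SAP 9.4.1 repeats that scope ("The proportion of returned rings (used and unused) during the 3-monthly clinical follow-up schedule will also be reported") and then gives the calculation: "This will be calculated as the number of used/unused rings returned divided by the number of rings dispensed". No visit, time window or link between individual rings is stated.

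The same section names the ring insertion/removal (RL) CRF as the source, "indicating the rings dispensed at each trial visit (items 1 and 2) and the used / unused rings returned at each trial visit". Shell Table 14.6.1 has a row "Number of used/unused rings returned" (m), a row "Number of rings dispensed" (M) and then m/M. All three sit under one Trial Month X heading, in columns for schedules A, B, C and all schedules. There is no row pooled over visits.

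The number of rings handed out changes by design. Protocol 4.2 gives one ring at enrolment. Protocol 4.3 then says: "Dispense one vaginal ring to participants during monthly visits and three vaginal rings during 3-monthly visits", with other arrangements allowed. Protocol 5.13 lets women who do not want spare rings at home collect and return them at interim visits.

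**The concern.** A ring handed out at one visit normally comes back at the next. Rings returned and rings dispensed at the same visit are therefore different rings, and their ratio depends on how many were handed out on each occasion as well as on whether women bring rings back. The planned step from one ring to three would look like poor return even if every ring came back. Conversely, a woman who takes three rings home and is never seen again adds nothing to either count at the next visit.

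At stake is how feasibility is described. Exploratory objective 1 asks whether 3-monthly follow-up could serve as a schedule after licensure, and whether rings taken home are returned bears on that.

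**Working it through.** The documents give no value for this proportion, so there is no figure to reproduce. The check counts rings under each possible reading.

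**Inputs**
- One ring dispensed at enrolment (Protocol 4.2), one at each monthly visit and three at each 3-monthly visit (Protocol 4.3; SAP 3.1).
- Visit months from SAP 6.6: A at 1, 4, 7, 10, 13; B at 1, 2, 5, 8, 11, 14; C at 1, 2, 3, 6, 9, 12; each followed by an exit visit. The switch to 3-monthly visits is at Month 1, 2 or 3.
- Assumed: Months 13, 14 and 12 are the last product use visits. Nothing is dispensed at that visit (Protocol Appendix A).

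**Same-visit ratio, every ring returned on time, all three rings taken**

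| Schedule | Before switch | At switch | Later visits with dispensing |
|---|---|---|---|
| A | none | Month 1: 1/3 = 33% | Months 4, 7, 10: 3/3 = 100% |
| B | Month 1: 1/1 = 100% | Month 2: 1/3 = 33% | Months 5, 8, 11: 3/3 = 100% |
| C | Months 1, 2: 1/1 = 100% | Month 3: 1/3 = 33% | Months 6, 9: 3/3 = 100% |

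**Women who take one ring at the switch.** If a fraction o take one ring, the ratio is 1/[3(1 − o) + o] = 1/(3 − 2o). For assumed o = 10%, 25% and 50% this is 1/2.8 = 36%, 1/2.5 = 40% and 1/2 = 50%.

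**All-schedules column at Month 1.** If a fraction a of women are on A and all A women take three rings, the ratio is 1/[3a + (1 − a)]. For assumed a = 90%, 75% and 50% this is 36%, 40% and 50%. With equal thirds it is (1 + 1 + 1)/(3 + 1 + 1) = 60%.

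**Loss between 3-monthly visits.** Let N women each take three rings and a fraction q not come back. At the next visit m = 3N(1 − q) and M = 3N(1 − q), so m/M = 100% for any q. Followed ring by ring, the proportion returned is 3N(1 − q)/3N = 1 − q, which is 95%, 90% or 80% for assumed q = 5%, 10% or 20%. For example, with N = 100 and q = 20% the same-visit ratio is 240/240 = 100%, while 240/300 = 80% of the rings dispensed came back.

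**Pooled over the 3-monthly period, every ring returned.** With k 3-monthly dispensings (k = 4 for A and B, 3 for C), the ratio is 3k/3k = 100% if the ring brought back at the switch is left out. If that ring is counted, it is (3k + 1)/3k = 13/12 = 108% for A and B, and 10/9 = 111% for C. Unreturned rings lower the pooled value.

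**Ring-linked, every ring returned.** 12/12 (A, B) and 9/9 (C), so 100%.

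Identical, perfect behaviour can therefore read 33%, 100%, 108% or 111%, depending on a choice that the SAP does not make.

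**The case against.** The strongest reply is that a same-visit definition appears nowhere in the SAP sentence. The stated scope is the 3-monthly schedule as a whole, and the m/M row label repeats that wording, so a pooled or ring-linked ratio also fits. That is correct, and it is why the point is an undefined denominator with a misleading shell. It does not clear the plan: the CRF counts are described per visit, the shell has a per-visit heading and no pooled row, and a programmer following it would most directly produce the same-visit figure.

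Four stronger conclusions are tempting and are not supported:
- **That the ratio fails throughout.** The 33% arises once per schedule, for women who take all three rings. The ring returned at that visit was dispensed before 3-monthly follow-up began, so the scope wording could be read to exclude it.
- **That the shell prints an undefined 3/0 at the last product use visit.** The m, M and m/M rows appear only in the first block of Table 14.6.1, alongside the question asked at Months 1 to 3. The follow-up and last-visit blocks do not carry them. Read literally, the ratio is printed around the switch and omitted later. The 100% that ignores lost women arises only if the rows are extended.
- **That unreturned rings are hidden.** If the rows are extended, the counts themselves show the gap: in the example above, 300 dispensed at one visit and 240 returned at the next. Listing 16.2.5.4 records return and the reason for non-return for each ring, Table 14.1.1.1 gives loss to follow-up by schedule, and Protocol 6.6 requires rings that could not be retrieved to be documented. Only the percentage fails to reflect them.
- **That interim-visit rings are dropped.** SAP 6.6 says "Data from scheduled visits will be presented in the summary tables", but Table 14.6.3 counts tests at unscheduled visits, and SAP 9.4.4 uses RL data from preceding unscheduled visits. Their treatment in this ratio is simply not stated.

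It is also fair to say that SAP 9.4.1 names the participant report as exploratory endpoint 1, with ring return an additional description and no test or decision attached.

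**Conclusion.** The point holds in a limited form. SAP 9.4.1 leaves the denominator open, and Table 14.6.1 leads towards a ratio of different rings. On that reading perfect return shows as 33% at one visit per schedule, or about 36% to 50% if 10% to 50% of women take one ring. If the rows are carried forward, the ratio stays at 100% whatever share of women fail to come back. A pooled ratio avoids the second fault but exceeds 100% if the ring returned at the switch is counted.

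The opt-out shares, loss rates, schedule mix and last-product-use months are assumptions; the 1/3 follows directly from the dispensing rule. The consequence is confined to an exploratory, descriptive measure. The change is still worth making, because following the shell gives a misleading figure for a listed assessment and the correction needs no new data.

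**What to change.** Define the proportion per ring, by dispensing visit, in SAP 9.4.1:
- Of the rings dispensed at each 3-monthly visit, report the percentage returned by the next scheduled visit and the percentage ever returned.
- Keep the rings of women who do not come back in the denominator.
- Exclude rings dispensed under the monthly schedule, or show them in a separate row.
- State that rings dispensed or returned at interim visits are counted.

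Move the m, M and m/M rows of Table 14.6.1 to match, so that they cover the 3-monthly visits. Listing 16.2.5.4 already holds the dispensing visit and return visit of each ring.

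The cost is SAP wording and one reprogrammed table section. The reported figure may be less favourable, because rings never returned will count against it.
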